3.5.2 Lead Extraction procedure

Personnel, tools, techniques, approaches, outcomes

- number of personnel
- cardiothoracic surgeon stand-by, presence of the surgeon at the procedure
- procedural room setting
- tools used
- techniques used
- approaches used
- type of anesthesia
- procedural time
- fluoroscopic exposure
- acute outcomes
- complications (major, minor, see definitions)

3.5.3 Post-procedure evaluation

Post-procedure and pre-discharge

- ECG and vital sign monitoring
- Echocardiographic evaluation
- Chest X-Ray
- Pharmacological and Antibiotic therapy
- In-hospital complications and mortality

3.5.4 Reimplantation and discharge

Need for reimplantation

- Type of CIED
- Acute Complications
- Investigations at discharge
- Therapy at discharge

3.5.5 Follow-up data

Twelve months follow-up is required to evaluate clinical failures of TLE procedures, endpoints and long-term complications.

3.5.5.1 Outcome even in case of failure or refusal

Follow-up is scheduled for all enrolled consecutive patients also in case of failure or refusal of the procedure.

3.6 DEFINITION OF SUCCESS, FAILURES, COMPLICATIONS AND MORTALITY

To compare the clinical efficacy of the treatment with regard to the complete extraction of lead we define:

- 1 - Radiological Success
- 2 – Clinical success based on achievement of clinical outcome according to “intention to treat”

3.6.1 Success

A - Radiological Success

Removal of all targeted leads and all lead material from the vascular space, with the absence of any permanently disabling complication or procedure related death

Total = complete

Partial = less than 4 cm remains in the cardiovascular system

B – Clinical success based on the achievement of clinical outcome according to intention to treat measured

Acutely

Long term (12 months)

3.6.2 Failures

Inability to achieve either complete radiological or clinical success, or the development of any permanently disabling complication or procedure related death.

Failures will be defined as radiological and clinical.

Major complications are considered clinical failures.

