3.6.3 Complications

Extraction events are classified as major complications or minor complications according to their severity, as described below.

3.6.3.1 Major complication: Any of the outcomes related to the procedure which is life threatening or results in death. In addition, any unexpected event that causes persistent or significant disability, or any event that requires significant surgical intervention. They are:

1. Death
2. Cardiac avulsion or tear requiring thoracotomy, pericardiocentesis, chest tube or surgical repair
3. Vascular avulsion or tear requiring thoracotomy, pericardiocentesis, chest tube or surgical repair
4. Pulmonary embolism requiring surgical intervention
5. Respiratory arrest or anesthesia related complication leading to prolongation of hospitalization
6. Stroke
7. Pacing system related infection of a previously non-infected site

3.6.3.2 Minor complication: Any undesired event related to the procedure that requires medical intervention or minor procedural intervention to remedy, and does not limit persistently or significantly the patient’s function, nor threaten life or cause death. They are:

1. Pericardial effusion non requiring pericardiocentesis or surgical intervention

2. Hemothorax not requiring a chest tube
3. Hematoma at the surgical site requiring reoperation for drainage
4. Arm swelling or thrombosis of implant vein resulting in medical intervention
5. Vascular repair near the implant site or venous entry site
6. Hemodynamically significant air embolism
7. Migrated lead fragment without sequelae
8. Blood transfusion related to blood loss during surgery
9. Pneumothorax requiring a chest tube
10. Pulmonary embolism not requiring surgical intervention

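### A lead remnant under 4 cm counts as both a partial radiological success and a radiological failure, and a surgically repaired venous entry-site tear meets both a major and a minor complication item

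*Protocol*

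**What the plan says.** **Radiological success and failure.** Section 3.6.1 A defines radiological success as "Removal of all targeted leads and all lead material from the vascular space", provided that no permanently disabling complication or procedure-related death occurs. It then grades that success. The total grade is equated with complete removal. The other grade reads "Partial = less than 4 cm remains in the cardiovascular system". Section 3.6.2 defines failure as "Inability to achieve either complete radiological or clinical success, or the development of any permanently disabling complication or procedure related death". It goes on to say that failures are to be defined in two domains, radiological and clinical, and that "Major complications are considered clinical failures".

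**Major and minor complications.** Section 3.6.3 classifies extraction events as major or minor by severity. Each class has a general definition followed by a list. Major item 3 is "Vascular avulsion or tear requiring thoracotomy, pericardiocentesis, chest tube or surgical repair". Minor item 5 is "Vascular repair near the implant site or venous entry site".

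**Where the definitions are used.** Section 3.2.1 makes major procedure-related complications, deaths included, the primary measure. Section 3.2.2 makes acute and chronic outcomes a secondary objective and foresees comparisons among centres, countries and volume groups.

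**The concern.** Categories meant to be alternatives should not both apply to the same result or event. Here one radiological result has two statuses, and one type of vascular event has two severity classes. The reported rate then depends on which sentence is applied.

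The first overlap affects the radiological success and failure rates. The second decides whether certain events enter the primary measure. Section 3.1 expects more than 100 centres. If sites resolve the wording differently, part of any centre or country difference could be a coding difference. That is a risk, not an established fact.

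**Working it through.** No formula decides the point. The check is to take one patient or event and apply each definition to it. Arithmetic is used only for size.

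**1. Remnant under 4 cm, no complication**

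| Text | Status |
|---|---|
| 3.6.1 A, core definition | Not a success: some lead material remains |
| 3.6.1 A, grades | Partial radiological success |
| 3.6.2, with complete meaning the total grade of 3.6.1 | Radiological failure |

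The opening words "Inability to achieve either complete radiological or clinical success" can be read in two ways. If missing either one is enough, this patient is a failure overall. If failure means achieving neither, a patient with clinical success is not a failure overall. The second reading does not settle the radiological status, because the following sentence has failure judged separately in each domain and the only radiological standard in 3.6.2 is complete success.

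Size: let f be the share with a radiological failure on any reading and s the share with a remnant under 4 cm.
- Failure rate if partial counts as success (3.6.1): f
- Failure rate if only complete counts (3.6.2): f + s
- Difference: (f + s) − f = s

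The protocol gives neither f nor s. Assuming s = 1% to 5%, the difference is 1 to 5 percentage points. That is 3000 × 0.01 = 30 to 3000 × 0.05 = 150 patients if all 3000 have an extraction. For example, f = 1% and s = 3% (both assumed) give 1% under one section and 1% + 3% = 4% under the other.

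**2. Vascular tear at the venous entry site, repaired surgically, full recovery**

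| Text | Status |
|---|---|
| Major item 3 | Met: a tear that needed surgical repair; the item sets no limit on location |
| Minor item 5 | Met: a vascular repair at the entry site; the item does not exclude tears |
| General definitions | Depend on whether the repair counts as significant surgery or as a minor procedural intervention |

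No sentence says which item prevails.

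Size: the protocol gives no frequency for such events, so the effect on the primary rate cannot be derived. For context, the one derived figure that uses this endpoint is the total of about 1600 in section 4 (3-point difference, 90% power, 5% type I error). With 2% against 5%, a two-sided test and equal groups (the last two are assumptions):

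n per group = [1.960 × √(2 × 0.035 × 0.965) + 1.282 × √(0.02 × 0.98 + 0.05 × 0.95)]² / 0.03² = 787, or 1574 in total.

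This agrees with the stated figure, which is not in dispute. At 2%, 3000 patients yield 3000 × 0.02 = 60 major events. As an illustration only, reclassification of 0.5 to 2 percentage points would move 15 to 60 events.

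**The case against.** **The severity definitions govern the lists.** Minor events are limited to those that need medical or small procedural treatment, without threat to life or lasting limitation. Major events include those that need significant surgery. Item 5 then reads naturally as local access-site repair and item 3 as a severe tear. This has force and narrows the overlap. It does not close it: item 3 names surgical repair without any threshold of severity or place, and the text nowhere makes item 5 an exception to it.

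**Total and partial are already distinguished.** Both rates can therefore be reported from the same data, and the outcome is secondary. That is true if the grade is recorded, and it limits the harm. It does not tell the analyst which rate is the radiological failure rate.

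**The safeguards may catch it.** Section 3.5 promises CRF definitions in an addendum that is not at hand, and section 5.1 has a monitor go through the protocol with each site before the start. These reduce the risk of divergent coding but do not reconcile the protocol text.

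**Stronger readings that the documents do not support:**
- A reader might infer that 3.6.2 contradicts itself by naming permanently disabling complications and then counting every major complication as a clinical failure. The conditions are joined by *or*, each sufficient alone, so a major complication with full recovery is a clinical failure under 3.6.2 on every reading. It follows that 2-3% of 3000, or 60-90 patients, is not a count of patients whose clinical status is in doubt. Section 3.6.1 B gives clinical success only in outline, and the explicit rule in 3.6.2 can be read as completing it.
- A reader might see another overlap in pneumothorax needing a chest tube (minor item 9). There is none: the chest tube in major items 2 and 3 is tied to an avulsion or tear.

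**Conclusion.** The point holds for two overlaps.

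The first is a plain contradiction between 3.6.1 and 3.6.2, and within 3.6.1 itself. The radiological failure rate is not uniquely defined and differs by the full share of partial removals: 1-5 percentage points if that share is 1-5%, which is an assumption. It concerns a secondary outcome.

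The second is narrower but touches the primary measure. Entry-site tears repaired surgically can be placed in either class. Neither the size nor the direction of the effect on a given comparison can be established from the protocol. A reader might infer that the primary complication rate is unreliable as a whole; the documents support only that one type of event has no unique class.

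**What to change.** 1. Reconcile 3.6.1 and 3.6.2 into one set of mutually exclusive radiological categories: complete; partial (remnant under 4 cm); failure (remnant of 4 cm or more, or a targeted lead left in place). Say which categories count as success. The existing condition on disabling complications and procedure-related death can stay in the definition or be stated separately; the contradiction does not require its removal.
2. Add to 3.6.3 that an event meeting any major item is counted as major, and limit minor item 5 to repairs that do not meet major item 3.
3. At most, add to 3.6.1 B a cross-reference to the rule in 3.6.2 that major complications are clinical failures.
4. Carry the same wording into the CRF addendum.

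The cost is a few sentences if this is done before the addendum is final. After sites have begun coding, affected cases may have to be queried, and some may not be recoverable.

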3.6.3 Complications

Extraction events are classified as major complications or minor complications according to their severity, as described below.

3.6.3.1 Major complication: Any of the outcomes related to the procedure which is life threatening or results in death. In addition, any unexpected event that causes persistent or significant disability, or any event that requires significant surgical intervention. They are:

1. Death
2. Cardiac avulsion or tear requiring thoracotomy, pericardiocentesis, chest tube or surgical repair
3. Vascular avulsion or tear requiring thoracotomy, pericardiocentesis, chest tube or surgical repair
4. Pulmonary embolism requiring surgical intervention
5. Respiratory arrest or anesthesia related complication leading to prolongation of hospitalization
6. Stroke
7. Pacing system related infection of a previously non-infected site

3.6.3.2 Minor complication: Any undesired event related to the procedure that requires medical intervention or minor procedural intervention to remedy, and does not limit persistently or significantly the patient’s function, nor threaten life or cause death. They are:

1. Pericardial effusion non requiring pericardiocentesis or surgical intervention

2. Hemothorax not requiring a chest tube
3. Hematoma at the surgical site requiring reoperation for drainage
4. Arm swelling or thrombosis of implant vein resulting in medical intervention
5. Vascular repair near the implant site or venous entry site
6. Hemodynamically significant air embolism
7. Migrated lead fragment without sequelae
8. Blood transfusion related to blood loss during surgery
9. Pneumothorax requiring a chest tube
10. Pulmonary embolism not requiring surgical intervention

3.6.4 Mortality

Total mortality will be classified into different groups, which will also be evaluated separately. All-cause death will be classified in the following groups:

1. Non-cardiovascular death, including unknown
 - a. non-sudden
 - b. sudden (trauma, homicide)
2. Cardiovascular death
 - a. cardiac
 - i. sudden (including arrhythmic, myocardial infarction)
 - ii. non-sudden
 - b. vascular (e.g. embolic, SAB, stroke, other)
 - i. sudden
 - ii. non-sudden
 -

3.6.5 Timing of Complications and Mortality

- **3.6.5.1 Intra-procedural:** Any event related to the performance of a procedure that occurs or becomes evident from the time the patient enters the operating room until the time the patient leaves the operating room. This includes complications related to the preparation of the patient, the delivery of anesthesia, and opening and closing the incision.
- **3.6.5.2 Post-procedural:** Any event related to the procedure that occurs or becomes evident **pre-discharge**.
- **3.6.5.3 Long-term: within 12 months**

3.6.6 Death and Complications Relationship

1. Indication related
2. TLE procedure-related
3. Treatment post-TLE related

4 STATISTICAL CONSIDERATIONS AND SAMPLE SIZE

All patients enrolled will be included in the analysis. Statistical tests may be carried out for exploratory purposes, as appropriate. Multivariable analysis may be used to explore relationship between baseline covariates and post-baseline endpoints, as appropriate.

About 3000 patients are estimated as needed either to make an experience solid enough to judge the quality of the study or to obtain a preliminary continental profile of patients undergoing a TLE procedure according to the collected information listed above. The major complication rates in larger centres are estimated to be around 2-3% and to be able to demonstrate a difference of 5 % in complication rate. To detect a difference of 3 % in major complication rates between patients treated at experienced versus less

experienced centres with a power of 90 % and a type I error of 5 %, a total sample size of approximately 1600 subjects is required.

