3.1 DURATION OF THE STUDY

It is anticipated that over 100 centres will participate in the registry. Each centre will register consecutive patients for a total of 3000 patients.

The study should commence recruitment of patients in October 2012 and finish in June 2013. In the event that less than 3000 patients are enrolled at that time the study can be continued until this number of enrollees is reached.

The number of centres involved in each country will be agreed upon in advance in consultation with the national coordinators who will have knowledge of clinical practices specific to each country. Follow up information will be collected for all patients after 12 months from the procedure. The “last patient last visit” should be conducted by the end of December 2013.

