3.3 PARTICIPATING CENTRES

Centres will be enrolled on a voluntary basis from all the European Countries.

Centres will be anonymous and stratified on the basis of their volume of activity:

High volume Centres:	> 30 pts/y
Medium volume Centres	15>30 pts/y
Low volume Centres	< 15 pts/y

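### The 1600 patients quoted for 90% power are too few for a comparison between types of centre: the figure needs a 2% reference rate, near-equal groups and no clustering by centre

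*Protocol*

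**What the plan says.** Protocol section 4 gives a reference rate: "The major complication rates in larger centres are estimated to be around 2-3" per cent. The same sentence mentions an aim "to be able to demonstrate a difference of 5 % in complication rate", with no sample size attached. The next sentence makes the power claim, with less experienced centres as the second group: "To detect a difference of 3 % in major complication rates between patients treated at experienced versus less". The error rates are set out as "with a power of 90 % and a type I error of 5" per cent, and the result is that "a total sample size of approximately 1600 subjects is required". It does not state sidedness, how patients divide between the two groups, or any allowance for centre.

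The enrolment target is separate and larger: "About 3000 patients are estimated as needed", justified mainly by a continental profile of patients. Section 3.1 adds that "It is anticipated that over 100 centres will participate in the registry", with recruitment from October 2012 to June 2013, extendable until 3000 is reached.

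Section 3.3 says that centres are "stratified on the basis of their volume of activity": high above 30 patients a year, medium 15 to 30, low below 15. It gives no number of centres per class. Section 4 does not say which classes count as experienced.

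**The concern.** The comparison is between kinds of centre, and every patient in a centre shares the same exposure. Outcomes within a centre are likely to be correlated, so patients carry less information about this contrast than the same number of independent patients. The two groups are also not formed by allocation. Their sizes depend on which classes are called less experienced and how many such centres join. A calculation that assumes near-equal groups of independent patients gives the most favourable answer on both counts, and this one also needs the lower end of the reference range.

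If the sentence stands, a volume comparison that finds no difference could be reported as having had 90% power when the actual power was lower. The protocol would also imply that 3000 leaves a comfortable margin over a requirement of 1600, when the margin depends on choices it has not made.

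**Working it through.** **Inputs from the protocol.** Reference rate p1 = 2% to 3%; difference d = 3 points, so p2 = 5% to 6%; power 90%; type I error 5% (taken as two-sided); planned N = 3000; about 100 centres, so 3000/100 = 30 per centre.

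**Assumed inputs.** Share s of patients at less experienced centres; ICC.

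**Formula (pooled variance, no continuity correction).** With pbar = (1-s)p1 + s p2, A = sqrt[pbar(1-pbar)(1/s + 1/(1-s))] and B = sqrt[p1(1-p1)/(1-s) + p2(1-p2)/s]:

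- N = (1.960 A + 1.2816 B)^2 / d^2
- power = Phi[(d sqrt(N_eff) - 1.960 A)/B]
- N_eff = N / [1 + (m-1) ICC], where m is the number of patients per centre

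**Step 1: reproduce 1600.** For 2% versus 5% in equal groups, n per group = [1.960 sqrt(2 x 0.035 x 0.965) + 1.2816 sqrt(0.02 x 0.98 + 0.05 x 0.95)]^2 / 0.03^2 = (0.5094 + 0.3320)^2 / 0.0009 = 786.6. That rounds up to 787 per group, 1574 in total. At 40:60 the total is 1608. So the figure reproduces with equal or near-equal groups and a design effect of 1. It is not based on the 5-point difference, which needs only 720 (2% versus 7%) to 870 (3% versus 8%).

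**Step 2: upper end of the reference range.** For 3% versus 6%, n per group = (0.5746 + 0.3747)^2 / 0.0009 = 1001.4, about 2003 in total. With 1600 in equal independent groups, power is 83%. A one-sided 5% test would need 1632 here, so 1600 could also come from that route. It too assumes equal groups and independence.

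**Step 3: clustering at 1600.** With ICC 0.01 and m = 30 the design effect is 1 + 29 x 0.01 = 1.29. Two groups of 800 then give 82% (2% versus 5%) or 72% (3% versus 6%). The total needed for 90% becomes 1574 x 1.29 = about 2030, or 2003 x 1.29 = about 2584. If 1600 patients were spread over 100 centres (m = 16), the design effect is 1 + 15 x 0.01 = 1.15 and power is about 86% / 77%, still below 90%.

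**Step 4: plausible shares.** Suppose one third of 100 centres fall in each class and recruitment lasts nine months. A low-volume centre at 14 a year supplies at most 14 x 0.75 = 10.5 patients, and 33.3 such centres supply 350, or 350/3000 = about 12%. Medium centres at 30 a year add 33.3 x 22.5 = 750, so low plus medium reach 1100/3000 = about 37%. These are ceilings under the assumed split. Recruitment over twelve months would raise them to about 16% (467/3000) and 49% (1467/3000).

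**Step 5: power at the planned 3000** (2% versus 5% / 3% versus 6%, m = 30).

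| Share less experienced | Independent | ICC 0.01 | ICC 0.05 |
|---|---|---|---|
| 50% | 99% / 98% | 98% / 94% | 82% / 72% |
| 37% (low + medium) | 99% / 97% | 97% / 92% | 81% / 71% |
| 20% | 95% / 90% | 90% / 83% | 70% / 60% |
| 12% (low only) | 87% / 78% | 79% / 69% | 58% / 48% |

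A common cluster size is a simplification. With 10 patients per less experienced centre and 40 per experienced centre, the 12% row at ICC 0.01 becomes 83% / 74%.

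**The case against.** The strongest reply is that no confirmatory result rests on 1600. The registry plans 3000, its primary objective is overall safety, section 3.2.2 lists centre comparisons only as possible evaluations, and section 4 calls statistical tests exploratory. At 3000 the comparison has at least 90% power over much of the range above. The analysis model for clustered data is normally left to the SAP, which is not at hand. All of this stands, and it limits the weight of the point. It does not make the sentence about 1600 and 90% correct for a contrast between centres.

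A reader might infer more than the protocol supports:

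- **That the volume classes force the less experienced group to be small.** Section 3.3 gives cut-offs but no centre counts, and section 4 does not map experience to a class. The group is clearly small only if it means low volume alone.
- **That 1600 requires exactly 800 + 800, and hence at least 72 low-volume centres.** A 40:60 split needs only 1608. The centre count also presumes a low-only group and a study of 1600.
- **That 3000 patients from 100 centres in nine months implies an average of 40 a year, so almost everyone is treated at a high-volume centre.** Recruitment can be extended. Over 18 months the average is 20 a year, and an average does not fix the share in each class.
- **That the analysis will treat patients as independent.** The protocol names no model. The criticism is of the sample-size calculation.

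**Conclusion.** The point holds for the stated sample size and power. Under a two-sided test, 1600 patients give 90% power only at the 2% end of the reference range, with near-equal groups and no within-centre correlation. The last condition is doubtful for a centre-level exposure. A modest ICC of 0.01 takes equal groups of 800 at 30 per centre to 82% / 72%, so the requirement is understated.

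The documents do not show that the registry is underpowered at 3000. If low and medium centres together form the less experienced group, with about 37% of patients, power stays above 90% at ICC 0.01 for both reference rates. It falls to 79% / 69% for a low-only group of about 12% at that ICC, and below 90% at every share shown at ICC 0.05. Shares, ICC and a common 30 patients per centre are assumptions. The missing mapping to volume classes would alone be a detail for the SAP. It matters here because the quoted power cannot be checked without it.

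**What to change.** Keep the target of 3000. In section 4:

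1. Name the contrast in the classes of section 3.3, for example high versus medium plus low.
2. Replace the 1600 / 90% statement with the power, or the detectable difference, at N = 3000. Give it over a stated range of patient shares, reference rates from 2% to 3%, and ICC values, and state sidedness.
3. Say that this comparison accounts for clustering by centre. The choice of model can be left to the SAP.
4. Remove the 5-point difference or tie it to its own calculation, so that one target difference is in force.

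The cost is one recalculation and a few sentences. The quoted power will be less favourable and the intervals for the centre comparison slightly wider. No extra patients are needed.
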